1st biopsy: 20 min after oral drink; 2nd biopsy: immediately following end of exercise bout 1. objective: metabolomic profiling of the state of the energy metabolic network in muscle and mapping of individual phenotypic muscle properties (fiber type, mitochondrial density, capillary density). Biopsies will be obtained from the m. vastus lateralis of the left leg. Hereto, a preparatory superficial incision of the skin and fascii will be made under local sedation and bandaged, allowing fast and reproducible biopsy sampling prior to and immediately following exercise bout 1 below.

- 40 min upright bicycling exercise at FATMAX outside MR scanner (exercise bout 1)

Blood samples are collected every 10 minutes.

- microbiopsy from the quadriceps muscle (optional)

Biopsy will be obtained from the m. vastus lateralis of the left leg (see above).

- 5 min supine bicycling exercise at 50% MVO_2 inside MR scanner (exercise bout 2)

*serial in vivo ^{31}P MR spectra will be recorded non-invasively from the m. vastus lateralis of the right leg as previously (protocols **12-211/K** (VLCAD; UMC Utrecht); **NL41313.042.12** (MCAD; UMG) to determine energy and proton balance in the muscle during exercise and the kinetics of metabolic recovery following exercise. A blood sample will be taken after the subject has exited the scanner room. Final blood samples including on-site analysis of CK levels are taken up to 3 hr post-session III to monitor any rhabdomyolytic event.*

- 24 hours after session II and III, co-investigator [name] will call each subject to evaluate subjective fatigue and muscle complaints after the subject left the test facility.

Time between study sessions I and II will be at least 7 days; time between study sessions II and III will be 7 days. For session I, patients will be asked to abstain from food 3 hrs prior to the test. For sessions II and III, participants will be asked to keep a 'food diary' for the week prior to the test in order to monitor the caloric intake and macronutrient content of each participant. For sessions II and III, patients will travel to Groningen the evening prior to the study and will be housed in a hotel across the street from UMCG. Patients are able to take a

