3. STUDY DESIGN

This is a randomised, blinded, placebo controlled, two-way cross over trial. Patients with VLCADD will be recruited by the VLCADD Expertise Center at UMC Utrecht. Nutritional ketosis will be compared to a placebo, delivered as an isocaloric drink before exercise. An individualised, standardised bicycle exercise protocol will be completed by each participant with collection of blood metabolites, respired gases, and subjective ratings of fatigue and muscle complaints. In addition in vivo ³¹P MR Spectroscopic recordings will be made from the quadriceps muscle before (resting), during and post-exercise. An optional muscle biopsy will be obtained from the quadriceps before and after exercise.

Patients will be asked to participate in three study sessions:

session I (site: nearest Academic Medical Center, Pediatric test ward).

- standard maximal cardiopulmonary exercise test (CPET; bicycle ergometry with indirect calorimetry)
objective: determination of VO_{2max} in order to set the desired exercise workload of maximal individual rate of fat oxidation (FATMAX; typically ~40% MVO_2) in sessions II and III below.
- venipuncture
objective: measure rise in blood lactate and creatine kinase (CK) levels in response to CPET

sessions II and III (site: Neuroimaging Magnetic Resonance Center UMC Groningen).

- venipuncture + canulation
objective: prepare subject for serial (every 10 min) blood sampling for off-site metabolic profiling
- oral intake of nutritional drink A or B (ketone and placebo drinks, respectively)
Each subject will receive both drinks over the course of the trial in a blinded fashion – i.e., if drink A in session II, then drink B in session III, and vice versa.
- microbiopsy from the quadriceps muscle (optional)
*1st biopsy: 20 min after oral drink; 2nd biopsy: immediately following end of exercise bout.
objective: metabolomic profiling of the state of the energy metabolic network in muscle and mapping of individual phenotypic muscle properties (fiber type, mitochondrial density, capillary density). Biopsies will be obtained from the m. vastus lateralis of the left leg. Hereto, a preparatory superficial incision of the skin and fascii will be made under local sedation and bandaged, allowing fast and reproducible biopsy sampling prior to and immediately following exercise bout 1 below.*

- 40 min upright bicycling exercise at FATMAX outside MR scanner (exercise bout 1)

Blood samples are collected every 10 minutes.

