Subjects state subjective fatigue and muscle ache following exercise bout.

- microbiopsy from the quadriceps muscle (optional)

Biopsies will be obtained from the m. vastus lateralis of the left leg (see above).

- 5 min supine bicycling exercise at FATMAX inside MR scanner (exercise bout 2)

*serial in vivo 31P MR spectra will be recorded non-invasively from the m. vastus lateralis of the right leg as previously (protocols **12-211/K** (VLCAD; UMC Utrecht); **NL41313.042.12** (MCAD; UMG) to determine energy and proton balance in the muscle during exercise and the kinetics of metabolic recovery following exercise. Subjective fatigue and muscle ache scores and a blood sample will be taken after the subject has exited the scanner room. Final blood samples including on-site analysis of CK levels are taken up to 3 hr post-session III to monitor any rhabdomyolytic event.*

- 24 hours after session II and III, co-investigator [name] will call each subject to evaluate subjective fatigue and muscle complaints after the subject left the test facility.

Time interval between study sessions I and II will be at least 7 days; between study sessions II and III: 7 days. The night prior to sessions II and III, patients will be housed in close vicinity to the UMCG. Patients will be instructed to take a late evening snack or meal according to their individual record of maximal fasting duration, given a start time of the study at 08:00 am the following day. Patients will be allowed a light breakfast according their normal diet before they will receive the caloric drive before the test. The breakfast will be the same for session II and III.

The total duration of the first session will be around 45 minutes, with 30 minutes of preparation and 8-12 minutes of cycling (exact time length dependent on the maximal endurance of the participant). The total duration of the second and third session will be around 5 hours including 45 minutes of preparation, 45-60 minutes of bicycling for the submaximal endurance exercise test and 3 hours of post-exercise resting where after the last blood and urine sample will be collected. During this 3 hour period, participants will be asked to fill out a HAES diary and can watch a DVD to pass time.

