4. STUDY POPULATION

4.1 Population (base)

Six patients with VLCADD between 16 and 65 years of age, seen by [name] for evaluation in the VLCADD expertise center of the UMC Utrecht.

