4.3 Exclusion criteria

- contraindications for MRI studies (assessed by standardised questionnaire as previously used in METC 08-267/K; see UMCG section F METC documents)
- inability to perform bicycle exercise.
- recent episode of rhabdomyolysis, or treatment for acute renal failure in the past 2 months.
- intercurrent illness which may influence exercise tolerance (anaemia, musculoskeletal injury, or other undiagnosed illness under investigation).
- known coronary artery disease, positive history for angina, or changes on ECG suggestive of previous ischaemia without a negative stress test.
- insulin-dependent diabetes mellitus.
- loss of, or an inability to give informed consent.
- pregnancy or current breastfeeding, or females not taking the oral contraceptive pill (this is due to the variability in hormonal patterns and substrate levels with different parts of the menstrual cycle).
- any other cause which in the opinion of the investigators, may affect the volunteers ability to participate in the study

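### Pill use is required of women to limit hormonal variability, but sessions II and III are not tied to pill phase, so the two drinks can fall in different hormonal states in a woman on a cyclic pill

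*Protocol*

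**What the plan says.** - **Who may enter.** The exclusion criteria in section 4.3 bar "females not taking the oral contraceptive pill". The reason follows in brackets: "this is due to the variability in hormonal patterns and substrate levels with different parts of the menstrual cycle". No pill type or regimen is specified.
- **Timing of the cross-over sessions.** Section 3 fixes the interval "between study sessions II and III: 7 days", and the Summary agrees: "time between study sessions II and III will be 7 days". The earlier gap has only a lower limit: "Time interval between study sessions I and II will be at least 7 days". Session II may therefore fall on any pill day.
- **Treatment by session.** One drink is given per session: "if drink A in session II, then drink B in session III, and vice versa". Each patient's drink contrast is thus also a contrast between two dates a week apart.
- **What is held constant.** "The breakfast will be the same for session II and III". Section 8.3 adds a food diary. Pill day, pill week and hormone-free days are not mentioned in the Summary, section 3 or section 8.3.
- **Size.** Section 4.1 plans for "Six patients with VLCADD between 16 and 65 years of age". The number of women is not given.

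**The concern.** In a cross-over trial, a nuisance factor that stays the same in both sessions cancels from the within-patient difference, and one that changes between sessions does not. Requiring the pill narrows the hormonal differences between women. It gives each woman the same state in both sessions only if the two dates fall in the same pill phase.

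The 7-day spacing is awkward here. If the hormone-free interval is itself 7 days long, a session in that week can never be paired with another session in the same week. Its partner always falls on active days.

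In a mismatched woman the drink effect and any pill-phase effect cannot be separated. With six patients, one such pair is 1/6, or about 17%, of the within-patient contrasts. The outcomes closest to the stated reason for the criterion are the blood substrates among the secondary endpoints in section 8.1.2. They also bear on the second objective, on substrate supply to muscle.

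Session timing belongs in the protocol and is not something normally left to a statistical analysis plan.

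**Working it through.** The protocol gives no figure on this point, so there is none to reproduce. The check counts calendar days.

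**Inputs from the protocol:** session III = session II + 7 days (section 3 and Summary); session II on any pill day (only a minimum gap after session I); six patients (section 4.1).

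**Assumptions, not in the protocol:** the pill regimen, varied below; every pill day equally likely for session II; the number of women, varied below.

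**Rule:** a start day is mismatched if exactly one of day d and day d + 7 (wrapped round the pill cycle) is hormone-free.

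**21 active / 7 free (free days 22–28)**
- Session II on days 1–14 puts session III on days 8–21: both active.
- Session II on days 15–21 puts session III on days 22–28: mismatched, 7 days.
- Session II on days 22–28 puts session III on days 1–7 of the next cycle: mismatched, 7 days.
- Total (7 + 7)/28 = 14/28 = 50%.

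**24 active / 4 free (free days 25–28)**
- Session II on days 18–21 puts session III on days 25–28: mismatched, 4 days.
- Session II on days 25–28 puts session III on days 4–7: mismatched, 4 days.
- Total (4 + 4)/28 = 8/28 = 29%.

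**Other regimens, same rule:** 84/7 gives 14/91 = 15%; 26/2 gives 4/28 = 14%; continuous use gives 0%.

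**Chance that at least one of w women is mismatched**, 1 − (1 − p)^w:

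| Women | 21/7 (p = 0.50) | 24/4 (p = 8/28) |
|---|---|---|
| 1 | 50% | 29% |
| 2 | 75% | 49% |
| 3 | 87.5% | 64% |

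With no women, or with continuous use only, the chance is 0.

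**Direction.** Mismatches are symmetric: with 21/7, 7 start days put the hormone-free week at session II and 7 put it at session III. With randomised drink order, the hormone-free session is equally likely to carry either drink, so the expected bias is zero. In a small sample the imbalance need not cancel. If orders are assigned independently, two mismatched pairs lean the same way with probability 2 × (1/2)² = 50%, and a single pair has nothing to offset it.

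**Would a different gap help?** With 21/7, gaps of 14 or 21 days still give 14/28 = 50%. A 28-day gap gives 0/28. Keeping 7 days and restricting session II to pill days 1–14 gives 0/14. The cause is the missing anchor to pill phase; the 7-day interval itself can stay.

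**The case against.** There is a good case that this is minor.

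1. **The stated reason concerns the menstrual cycle, not the pill cycle.** A reader might infer that the protocol itself says substrate levels differ between active and hormone-free pill days. It does not. Section 4.3 explains why women off the pill are excluded. The criterion may be meant to reduce variability without removing it. This stands: that pill phase matters is an inference from the sponsor's rationale, not a statement in the document.
2. **No effect on the main endpoints is shown.** Section 8.1.1 names intramuscular Pi, PCr and pH and the recovery rate constants. Section 4.4 speaks of detecting differences of at least 30% in such parameters. Nothing in the protocol sizes a pill-phase effect on any of them. This stands.
3. **Mismatch may never occur.** A reader might infer that the two drinks will often fall in different phases. That requires women to be enrolled and to use a cyclic pill, and the protocol states neither. Depending on regimen, the figure runs from 0 to 50%. This stands, and the point must be put conditionally.
4. **Randomised order protects against bias.** A reader might infer a biased treatment comparison. The symmetry shown above and the randomisation in section 8.2 rule that out in expectation. What remains is confounding within a mismatched woman, and noise or chance imbalance across the six patients.
5. **Few patients can still benefit.** Section 1, on adolescent patients, reports that four had taken part 1.5 years after the first inclusion and that the lower age limit opens the study to one more, whose sex is not given. With six planned, 6 − 4 = 2 places remained at that point. This stands and limits the gain.

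None of this supplies the missing scheduling instruction. The plan keeps breakfast constant across sessions but leaves pill phase free, although it treats hormonal variability as reason enough to exclude patients with a rare disease.

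**Conclusion.** The point holds in a conditional form. The plan requires pill use to limit hormonal and substrate variability but does not place sessions II and III in the same pill phase. In a woman on a cyclic pill the two drinks can therefore fall in different hormonal states, and her drink contrast is then mixed with pill phase.

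The size is a mismatch on 50% of start days under an assumed 21/7 regimen, 29% under 24/4, about 14–15% under 26/2 or 84/7, and 0% under continuous use. All of these assume that session II is equally likely on any pill day. They measure how often the calendar mismatches, not how far an endpoint would move, which the protocol gives no means of estimating. The number of women and their regimens are unknown, and with no women the issue disappears.

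The documents do not support a claim of systematic bias or of likely damage to the 31P MRS results. This is an avoidable source of within-patient confounding that is cheap to remove, and it should be ranked as a small improvement.

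**What to change.** Add one scheduling rule to sections 3 and 8.3. For any woman still to be tested whose pill has a hormone-free interval, book session II so that both sessions fall on active-pill days. With a 21/7 regimen this means session II on pill days 1–14, which keeps the 7-day gap. Record the regimen and the pill day at each session. For patients already tested, report pill day where source records allow.

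The rule leaves eligibility, each woman's own pill use and the study procedures unchanged. The open-ended gap between sessions I and II already leaves room for it. Lengthening the gap to 14 or 21 days would not serve instead.

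Cost: with 21/7, half the days of a pill cycle are available for session II, so booking may slip by up to about two weeks (from day 15 to day 1 of the next cycle is 14 days). The gain is limited to the few patients not yet tested. For the others, pill day can only help to interpret individual results, and only if it was recorded.

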4. STUDY POPULATION

4.1 Population (base)

Six patients with VLCADD between 16 and 65 years of age, seen by [name] for evaluation in the VLCADD expertise center of the UMC Utrecht.

4.2 Inclusion criteria

- Confirmed VLCADD by genetic profiling.
- age 16-65.

4.3 Exclusion criteria

- contraindications for MRI studies (assessed by standardised questionnaire as previously used in METC 08-267/K; see UMCG section F METC documents)
- inability to perform bicycle exercise.
- recent episode of rhabdomyolysis, or treatment for acute renal failure in the past 2 months.
- intercurrent illness which may influence exercise tolerance (anaemia, musculoskeletal injury, or other undiagnosed illness under investigation).
- known coronary artery disease, positive history for angina, or changes on ECG suggestive of previous ischaemia without a negative stress test.
- insulin-dependent diabetes mellitus.
- loss of, or an inability to give informed consent.
- pregnancy or current breastfeeding, or females not taking the oral contraceptive pill (this is due to the variability in hormonal patterns and substrate levels with different parts of the menstrual cycle).
- any other cause which in the opinion of the investigators, may affect the volunteers ability to participate in the study

4.4 Sample size calculation

Exact sample size calculation for this study is difficult for several reasons:

1. VLCADD is a rare metabolic disorder. The UMCU Center currently has 6 patients that may qualify for this particular study.
2. The proposed study is the very first of its kind. No equivalent means of imposing acute NK has previously been available. As such, there are no data available on the magnitude of any enhancement effect of the nutritional intervention on metabolic performance in this particular group of patients.

As mentioned in Section 3, this study is a randomised, blinded, placebo controlled, two-way cross over trial. In previous case-control design studies, it has been well established that $\geq 30\%$ differences in the two categories of MRS-derived metabolic parameters – i.e., steady-state muscle pH, Pi and PCr levels, and kinetic rate constants of metabolic recovery post-exercise - can be reliably and reproducibly identified by the proposed investigational methods (e.g. [18]). We previously successfully detected statistically significant abnormalities in muscle MRS parameters ($P < 0.05$; two-sided) in a case-control study of VLCADD featuring 5 patients (Diekman et al, PloS One 2016).

5. TREATMENT OF SUBJECTS

5.1. Investigational product/treatment

Nutritional drink and placebo (“sports drinks”).

5.2. Use of co-intervention

Prolonged moderate-intensity exercise.

5.3. Escape medication

In case of physical complaints, the exercise will be terminated prematurely. Paracetamol is available if needed by the patient. Additionally, dextrose tablets will be available to administer when clinical symptoms of hypoglycaemia (e.g. headache, or light headedness) occur.

6. INVESTIGATIONAL MEDICINAL PRODUCT

This section is not applicable for this study.

7. NON-INVESTIGATIONAL PRODUCT

This section is not applicable for this study

8. METHODS

8.1 Study parameters/endpoints

8.1.1 Main study parameter/endpoint

- (i) steady-state in vivo intramuscular levels of Pi, PCr, and pH during exercise versus rest.
- (ii) kinetic rate constants of metabolic recovery post-exercise.

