The effect has been attributed to enhanced muscle mitochondrial function in addition to glycogen sparing. Here, we will investigate if acute NK in adolescent and adult symptomatic VLCAD deficient patients can boost muscle mitochondrial function in vivo. If so, a rational basis will have been established for therapeutic use in this metabolic myopathy. This study will include patients from the age of 16 years that could benefit from NK as well. Since rhabdomyolysis often has an onset in adolescence, confirmation of our hypothesis would lead to therapeutic use in that age group as well. Moreover, older patients often suffer from severe exercise intolerance and loss of muscle function due to earlier episodes of rhabdomyolysis, leaving most of them unable to complete our study protocol. Due to the rarity of the disease and earlier argumentation, it's vital to include adolescent subjects to reach sufficient power in this study. As such, this study constitutes a vital first step towards possible validation of an effective treatment for patients with VLCADD that may improve the quality of life including an active lifestyle with overall health benefits.

Objective: To test if acute NK boosts muscle mitochondrial function in vivo in patients with VLCADD in order to establish a rational basis for therapeutic use in this disorder. A secondary objective is to gather data to test the working hypothesis that the positive effect of acute NK on muscle mitochondrial function results from enhanced substrate supply to the tricyclic acid (TCA) cycle.

Study design: randomised, blinded, placebo controlled, 2-way cross over trial.

Study population: Six Patients with VLCADD between 16 and 65 years of age, seen for evaluation in the VLCADD expertise centre of the UMC Utrecht.

Intervention (if applicable): Oral intake of nutritional drinks; prolonged moderate-intensity exercise on bicycle ergometer; in vivo Magnetic Resonance Spectroscopy; muscle microbiopsy; venipuncture.

Main study parameters/endpoints:

- Whole body:
 - Physical performance during a 45 bicycle exercise test at individual FATMAX workload (typically of the order of 40%MVO₂). Specifically:
 - completion of 40 min upright exercise bout at FATMAX workload (yes/no; if no, #minutes)
 - completion of 5 min in-magnet exercise bout at FATMAX workload (yes/no; if no, #minutes)
 - subjective fatigue and muscle ache score after each exercise bout (scale 0-10) and 24 hours after session (telephone consultation)

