2. OBJECTIVES

1. To investigate the potential of a novel dietary substrate preparation to enhance muscle mitochondrial function in VLCADD via acute nutritional ketosis.
2. To investigate if tri-citric acid cycle substrate supply in muscle of patients with VLCADD is boosted by acute nutritional ketosis.

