10 STATISTICAL ANALYSIS

10.1. Descriptive statistics

Data will be expressed both quantitatively (values of PCr, ATP, Pi, pH, rate constants tau_PC_r and tau_Pi, expressed as median and range), and qualitatively (MRS-spectra).

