10.2 Univariate analysis

Results will be presented by means of confidence intervals. The significance level will be set at $p < 0.05$. Statistical analysis of the results will be performed using standard two-sided Mann-Whitney testing and will be conducted using Origin software (Caltech, USA, version 6.1).

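### The Summary and section 8.1 disagree on which endpoints are main, and none of the five or more main MRS parameters in 8.1.1 is named as deciding objective 1

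*Protocol*

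**What the plan says.** Objective 1 (Protocol, section 2) reads "To investigate the potential of a novel dietary substrate preparation to enhance muscle mitochondrial function in VLCADD via acute nutritional ketosis". The Summary puts it more strongly: it sets out to test whether ketosis has this effect, and its Rationale says that if it does, "a rational basis will have been established for therapeutic use in this metabolic myopathy".

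Section 8.1.1 lists two main items: "steady-state in vivo intramuscular levels of Pi, PCr, and pH during exercise versus rest" and "kinetic rate constants of metabolic recovery post-exercise". It does not number the recovery constants. Section 10.1 names "rate constants tau_PC_r and tau_Pi"; the Summary lists recovery of PCr, Pi and pH. Section 4.4 gives no sample size calculation and relies on earlier experience with "differences in the two categories of MRS-derived metabolic parameters", without singling out either category.

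Section 10.2 states "Results will be presented by means of confidence intervals", sets significance at p < 0.05 and plans "standard two-sided Mann-Whitney testing".

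The Summary's own list of main parameters contains essentially the same MRS content. It adds completion of both cycling bouts, fatigue and ache scores, HAES, optional muscle metabolites, a blood panel including CK, and urine myoglobin. Section 8.1.2 classes most of these additions as secondary.

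**The concern.** Two faults meet here. First, current text contradicts current text on what is main. Second, even within 8.1.1 nothing says whether one parameter, any parameter or all of them must differ between drinks for objective 1 to be met.

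The Summary attaches a consequential claim to a positive answer. If no deciding parameter is fixed, that claim can be hung on whichever MRS result turns out favourable. Section 8.2 keeps the MRS analyst unaware of drink order. That protects the measurements, but not a later selection among finished results.

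The choice has substance because section 1 points in two directions. It rates the PCr and Pi recovery constants as the best available indices of mitochondrial function in vivo. It also reports that the team's earlier VLCADD work found no evidence of impaired mitochondrial ATP synthesis, and that the abnormality lay in Pi and PCr changes during exercise, three times those of controls.

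**Working it through.** **1. Main parameters in 8.1.1.** Pi, PCr and pH (exercise versus rest) = 3. Recovery constants named in 10.1 = 2. Total 3 + 2 = 5. With the Summary's three recovery measures it would be 3 + 3 = 6.

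**2. Summary list against section 8.1.**

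| Summary line (labelled main) | Status in 8.1 |
|---|---|
| Resting MRS levels; exercise MRS levels; MRS recovery (3 lines) | Main (8.1.1) |
| Completion of the 40-minute bout | Secondary (8.1.2) |
| Completion of the 5-minute in-scanner bout | Secondary (8.1.2) |
| Fatigue and ache scores | Secondary (8.1.2) |
| Optional muscle metabolites | Secondary (8.1.2) |
| Blood panel | Secondary (8.1.2), except CK, which is absent |
| HAES | Absent |
| Urine myoglobin | Absent |

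That is 3 + 7 = 10 lines. Of the seven non-MRS lines, 4 are secondary, 1 is secondary except for CK, and 2 are absent. Blood gas in the Summary overlaps blood pH in 8.1.2, so it is not counted as a conflict. In the other direction, acetoacetate is in 8.1.2 but not in the Summary.

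**3. What the open choice could do to the error rate.** The protocol gives no error rate or power figure to reproduce, so this is illustrative.

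Inputs from the protocol: two-sided Mann-Whitney at p < 0.05 (10.2) and six patients, each taking both drinks (4.1, 8.2). Five patients is also considered: section 1 says four had participated and that the lower age limit makes one more possible, 4 + 1 = 5.

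Assumptions: five null, normally distributed parameters; correlation between parameters from 0 to 0.7; within-patient correlation between the two sessions from 0 to 0.8. The protocol supplies none of these.

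Exact attained size of one test, if the two sets of values were independent: 38/924 = 0.041 for 6 v 6 and 8/252 = 0.032 for 5 v 5. With all parameters independent, the chance of at least one significant result is 1 − (1 − 0.041)^5 ≈ 0.189 and 1 − (1 − 0.032)^5 ≈ 0.15. Simulation (100,000 trials per cell) agrees at that corner and gives the rest:

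| Within-patient correlation | Any of five, n = 5 | Any of five, n = 6 | One named, n = 5 | One named, n = 6 |
|---|---|---|---|---|
| 0 | 0.110–0.151 | 0.137–0.190 | 0.032 | 0.041 |
| 0.3 | 0.061–0.077 | 0.075–0.098 | 0.016 | 0.020 |
| 0.5 | 0.035–0.041 | 0.041–0.051 | 0.008 | 0.010 |
| 0.8 | 0.006–0.007 | 0.007–0.008 | 0.001 | 0.002 |

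Ranges run over the correlation between parameters. The rates fall down the table because the unpaired test ignores that both values come from the same patient. No rule for several endpoints is at work.

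**The case against.** **Section 8.1 is the operative text.** It separates main from secondary clearly, and 4.4 rests on the same two MRS categories. The Summary list is arranged by whole body, muscle, blood and urine, and can be read as an inventory of everything measured. This stands as a matter of proportion: that half of the point is a labelling correction. It remains a correction to make, because the Summary's heading does call all ten lines main. Section 3 already ties CK to monitoring for rhabdomyolysis, so part of its role is stated.

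**The study is an early mechanistic one.** It has six patients, no prior effect data and a cautiously worded objective in section 2. Several co-reported MRS measures are easier to defend here than in a confirmatory trial. That is fair, but the Summary still links a positive answer to a basis for therapeutic use, and that link needs a result named in advance.

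**Multiplicity rules may sit in a SAP.** Agreed: the absence of a testing order or adjustment is not part of this point. The choice of main parameter and the conflict with the Summary are fixed in the protocol itself.

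**A stronger reading is tempting:** that five tests at 0.05 give a family-wise error of 1 − 0.95^5 = 0.226, or always at least double the nominal level. The documents do not support this. It assumes that any one significant parameter counts as success, which the protocol never says. It also ignores the discreteness of the test and the pairing of the data. At the within-patient correlations that a crossover is normally chosen to exploit, the any-of-five rate under the planned test can be at or below 5%.

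**Conclusion.** The point holds in two parts. The conflict between the Summary and 8.1 is a matter of record and needs no assumption. The lack of a deciding parameter also stands on the text: at least five parameters share main status, and sections 2, 4.4, 8.1 and 10 do not say which settles objective 1.

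The harm is that the result carrying the therapeutic-basis claim can be chosen after the data are seen. No single error figure should be attached to it, since the rates depend wholly on assumed correlations. What holds in every scenario examined is that choosing freely among five raises the false-positive chance above that of one named parameter, by at most a factor of five.

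A reader might also infer that PCr recovery is the only proper choice. Section 1 does not support that, since it gives grounds for the recovery constants and for the exercise changes. The protocol should be corrected on this point; the design and measurements are unaffected.

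**What to change.** 1. In 8.1.1, name one deciding parameter for objective 1, expressed as a difference between drinks, and justify it from section 1. The two natural candidates are the PCr recovery rate constant (closest to mitochondrial function, but in a pathway where section 1 reports no impairment) and the exercise-versus-rest change in PCr (where section 1, for Pi and PCr, reports the abnormality). The choice is the sponsor's.
2. Label the remaining MRS parameters supportive.
3. Align the Summary with 8.1.1 and 8.1.2, and state the role of CK and urine myoglobin (for example safety monitoring) and of HAES (for example descriptive).
4. Record when the choice was made and whether anyone making it had seen results by drink. If so, report the result as exploratory. A statement that the choice was blind may not be available: section 1 says four patients had already participated, and under 8.2 the person who records drink order also conducts the sessions with the principal investigator.

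Cost: one amendment notified to the METC (12.3), with no change to visits, measurements or sample size. The price is that an effect seen only in the other MRS parameters would count as supportive.
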